## **6.3 Potential risks of genetic testing**

Samples obtained for future research may include a search for genetic correlates of COVID-19 susceptibility or severity. Specimens will be labeled by study IDs, rather than names. This information will not be released to participants and will not become part of their medical records. Risks related to discrimination or other problems are deemed highly unlikely.

## **6.4 Alternatives**

The alternative to participation in this study is routine care and monitoring following close contact with an individual with COVID-19 or enrollment in a different clinical trial.

## **6.5 Infection prevention and control measures**

Care will be taken throughout the study to minimize the risk of transmission of the SARs-CoV-2 virus during study visits.

1. Participants will be provided with a surgical mask upon entry to the medical center and asked to wear a mask during their visit (other than during nasal swabbing) and during transit to and from the study site.
2. Participants will be asked not to use public transportation during the first two weeks of the study and will be provided with transportation reimbursement to study visits in a single occupancy vehicle.
3. Study staff will wear surgical masks, eye protection, gown and gloves during visits with study participants during visits -1 to 30 and at any time that community transmission of SARS-CoV-2 is reported by the

NYS Department of Health.

4. Scheduling of visits will be done with the goal of minimizing wait times at the study site.
5. Participants will be immediately placed in single exam rooms upon arrival.
6. All areas of participant contact will be wiped down with an approved viricidal agent after each visit. Doorknobs and other high touch areas will be cleaned at regular intervals as per medical center IPC guidelines.
7. At the clinician's discretion, face to face interactions may be minimized by collection of data from participants by phone or by telemedicine (using Zoom HIPAA compliant conferencing)
8. All clinical specimens will be transported according to hospital policy in biohazard bags using clinical carriers.

## 6.6 Safety monitoring

1. Safety evaluations will assess for the safety of anti-SARS-CoV-2 plasma and determine if risks are higher, lower or the same as control (albumin 5%)
2. Clinical evaluations: Vital signs and symptom screen on days -1, 0, 3, 7, 14 and symptom screens on days 1, 28 and 60. Parameters requiring referral for urgent medical care are included in each evaluation
3. Safety laboratory tests, including ABO blood type (day -1) pregnancy testing (day -1), CBC and comprehensive metabolic panel (days -1, 7 and 14), will be performed at the local CLIA-certified clinical laboratory

## 6.7 Adverse Event Reporting

An **Adverse Event (AE)** is any untoward or unfavorable medical occurrence in a human subject, including any abnormal sign, symptom or disease, temporally associated with the subject's participation in research, whether or not considered related to the subject's participation in the research.

**Serious Adverse Event (SAE):** any adverse event temporarily associated with the subject's participation in research that meets any of the following criteria:

- Results in death;
- Is life-threatening (places the subject at immediate risk of death from the event as it occurred);
- Requires inpatient hospitalization or prolongation of existing hospitalization;
- Results in a persistent or significant disability/incapacity;
- Results in a congenital anomaly/birth defect; or
- Any other adverse event that, based upon appropriate medical judgment, may jeopardize the subjects' health and may require medical or surgical intervention to prevent one of the other outcomes listed in this definition.

An **Unanticipated Problem (UP)** is any incident, experience or outcome involving risk to subjects or others in any human subjects research that meets all of the following criteria:

- Unexpected (in terms of nature, severity or frequency) given (a) the research procedures that are described in the IRB-approval protocol and informed consent document, and (b) the characteristics of the subject population being studied;
- Related or possibly related to participation in such research (i.e., there is a reasonable possibility that the incident, experience or outcome may have been caused by the procedures involved in such research); and
- Suggests that the research places subjects or others at a greater risk of harm (including physical, psychological, economic or social harm) than was previously known or recognized

A **Suspected Adverse Reaction (SAR)** is any AE for which there is a reasonable possibility that it was caused by the drug.

Reasonable possibility means that there is evidence to suggest a causal relationship between the drug and the AE. Examples of reasonable possibility are:

- A single occurrence of an event that is uncommon and known to be strongly associated with drug exposure.
- One or more occurrences of an event that is not commonly associated with drug exposure, but is otherwise uncommon in the population exposed to the drug.
- An aggregate analysis of specific events observed in a clinical trial that indicates that those events occur more frequently in the drug treatment group than in a concurrent or historical control group.

The S-I must report the following SARs:

- To the FDA, as soon as possible, but no later than 7 calendar days after the S-I's initial receipt of the information, any **unexpected fatal or life-threatening SAR**.
- To the FDA and all participating investigators, as soon as possible but no later than 15 calendar days after the S-I determines that information qualifies for reporting, in an IND safety report, **any SAR that is both serious and unexpected**.
- To the FDA and all participating investigators, as soon as possible but no later than 15 calendar days after the S-I determines that the information qualifies for reporting, **any findings from epidemiological studies, pooled analysis of multiple studies or clinical studies, whether or not conducted under an IND or by the S-I, that suggest a significant risk in humans exposed to the drug**.
- To the FDA and all participating investigators, as soon as possible, but no later than 15 calendar days after the S-I determines that the information

qualifies for reporting, **any findings from animal or *in vitro* testing, whether or not conducted by the S-I, that suggest a significant risk in humans exposed to the drug.**

- To the FDA and all participating investigators, as soon as possible, but no later than 15 calendar days after the S-I determines that the information qualifies for reporting, **any clinically important increase in the rate of a Serious SAR over that listed in the protocol or Investigator Brochure.**
- Expected SAEs and AEs should be included in the IND Annual Reports.

**Follow-up** information to a safety report should be submitted as soon as the relevant information is available. However, if the results of a sponsor's investigation show that an adverse drug experience not initially determined to be reportable are so reportable, the sponsor must report such experience as soon as possible, but no later than 15 calendar days after the determination is made.

**To IRB:**

1. Unanticipated Problems (UPs) must be reported promptly, but not later than 7 calendar days following the occurrence of the UP or the Principal's Investigator's acquiring knowledge of the UP.
2. Expected AEs must be reported at the time of continuing review of a protocol.

**Reporting Interval:**

All AEs and SAEs will be documented from the first administration of study product. All AEs and SAEs will be followed until resolution even if this extends beyond the study-reporting period. Resolution of an adverse event is defined as the return to pre-treatment status or stabilization of the condition with the expectation that it will remain chronic.

At any time after completion of the study, if the investigator becomes aware of a SAE that is suspected to be related to study product.

**Investigator's Assessment of Adverse Events:**

The determination of seriousness, severity, and causality will be made by an on-site investigator who is qualified (licensed) to diagnose adverse event information, provide a medical evaluation of adverse events, and classify adverse events based upon medical judgment. This includes but is not limited to physicians, physician assistants, and nurse practitioners.

Laboratory abnormalities will be reported as AEs if they generate medical intervention (treatment and/or procedures) or are considered clinically

significant and are not linked to a reported clinical AE. If a laboratory abnormality is related to a clinical AE, grading will be related to clinical AE. The grading of the laboratory AEs will be based on the toxicity tables in the Common Terminology Criteria for Adverse Events (CTCAE) version 5, Nov 27, 2017.

#### **Assessment of Seriousness:**

- I. Event seriousness will be determined according to the protocol definition of an SAE
- II. Assessment of Severity

Event severity will be assigned according to the Toxicity Tables. For parameters not included in the Toxicity Table the following definitions will be used:

- 1 = Mild: Transient or mild discomfort (<48 hours); no medical intervention/therapy required.)
- 2 = Moderate: Mild to moderate limitation in activity-some assistance may be needed; no or minimal medical intervention/therapy required)
- 3 = Severe: Marked limitation in activity, some assistance usually required; medical intervention/therapy required, hospitalizations possible
- 4 = Life-threatening: Extreme limitation in activity, some assistance usually required; medical intervention/therapy required, hospitalization or hospice care probable
- 5= Death

#### **Assessment of Association:**

The association assessment categories that will be used for this study are:

- Associated – The event is temporally related to the administration of the study product and no other etiology explains the event.
- Not Associated – The event is temporally independent of the study product and/or the event appears to be explained by another etiology.

The investigator must provide an assessment of association or relationship of AEs to the study product based on:

- Temporal relationship of the event to the administration of study product;
- Whether an alternative etiology has been identified;
- Biological plausibility;
- Existing therapy and/or concomitant medications.

## **7 SAFETY OVERSIGHT**

### **7.1 Monitoring Plan**

1. All AEs and SAEs will be reviewed by the study team in real time.
2. A data safety monitoring board (DSMB) composed of independent experts without conflict of interests will be established. The Board will review the

study before initiation and quarterly thereafter. The Board will review study data to evaluate the safety, efficacy, study progress, and conduct of the study

## **7.2 Study monitoring**

As per ICH-GCP 5.18 and FDA 21 CFR 312.50, clinical protocols are required to be adequately monitored by the study sponsor. Monitors will verify that:

- (1) There is documentation of the informed consent process and signed informed consent documents for each subject
- (2) There is compliance with recording requirements for data points
- (3) All SAEs are reported as required
- (4) Individual subjects' study records and source documents align
- (5) Investigators are in compliance with the protocol.
- (6) Regulatory requirements as per Office for Human Research Protections-OHRP), FDA, and applicable guidelines (ICH-GCP) are being followed.

## **7.3 Halting Criteria for the Study**

The study enrollment and dosing will be stopped and an ad hoc review will be performed if any of the specific following events occur or, if in the judgment of the study physician, subject safety is at risk of being compromised:

1. Unexpected death of a dosed subject in relation to infusion
2. Occurrence of a life-threatening allergic/hypersensitivity reaction (anaphylaxis), manifested by bronchospasm with or without urticaria or angioedema requiring hemodynamic support with pressor medications or mechanical ventilation.
3. One subject with an unexpected SAE associated with study product.
4. Two subjects with a Grade 3 or higher toxicity for the same parameter associated with study product.
5. An overall pattern of symptomatic, clinical, or laboratory events that the DSMB consider associated with study product and that may appear minor in terms of individual events but that collectively may represent a serious potential concern for safety.
6. Any other event(s) which is considered to be a serious adverse event in the good clinical judgment of the responsible physician. This will be appropriately documented.

Furthermore, given that ADE may be an issue with convalescent antibody treatment, out of an abundance of caution we will monitor the number of subjects in each trial arm that progresses to an indication for need of mechanical ventilation. In monitoring the number of subjects that progresses to this stage, we will present these data to the DSMB masked so that they may objectively evaluate and determine whether they would like to be unmasked. After at least 50% of trial participants have accumulated follow-up, the number of subjects that progress to this stage will be presented to the masked DSMB and formally asked whether they (1) see a clinically meaningful difference between trial arms that trigger an unmasking of the

DSMB and (2) if so do they require a formal interim analysis. At any point should the DSMB asked to be unmasked and require a formal interim analysis, we will examine the difference in treatment arms for need for mechanical ventilation. This interim analysis will adjust for factors related to need for mechanical ventilation including age and presence of cardiopulmonary comorbidities.

Upon completion of this review, DSMB will determine if study entry or study dosing should be interrupted or if study entry and study dosing may continue according to the protocol. Should the trial not be stopped at this time point, the final analysis would need to account the number of interim analyses that were conducted.

Therefore, we would penalize any final analysis dividing our 0.05 alpha in half for each interim analysis.

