## 3 STATISTICAL CONSIDERATIONS

### 3.1 Design Overview

This is a double-blinded, randomized phase 2 trial to evaluate the efficacy and safety of human SARS-CoV-2 immune plasma in individuals who are close contacts to person with COVID-19 within 7 days according to the CDC definition. This will also serve as an internal pilot in the seamless phase 2/3 study.

Eligible participants will be randomized to receive high-titer anti-SARS-CoV-2 immune plasma or control (albumin 5%) in a 2:1 ratio. We plan to enroll a total of 150 participants, with a maximum of 100 receiving the plasma and 50 receiving the control.

Each participant will be followed for 28 days after randomization and treatment, and will be tested and evaluated at baseline and on Days 3, 7, 14, 28 using a seven-category severity scale:

1. Not hospitalized, negative PCR for SARS-CoV-2
2. Not hospitalized, positive PCR for SARS-CoV-2 without symptom
3. Not hospitalized, positive PCR for SARS-CoV-2 with symptoms
4. Non-ICU hospitalization, not requiring supplemental oxygen
5. Non-ICU hospitalization, requiring supplemental oxygen
6. Requiring mechanical ventilation and/or in ICU
7. Death

The primary study endpoint is the rating on Day 28, or last rating evaluated. We will also consider time to various dichotomizations on this scale as secondary

outcomes, including time to death, time to requiring critical care, and time to requiring hospitalization

Other endpoints include:

- Anti-SAR-CoV-2 titers (Days 3, 7, 14, 28, 90 in addition to baseline)
- SAR-CoV-2 PCR positivity (Days 0, 3, 7, 14, 28 in addition to baseline)
- SAR-CoV-2 RNA (Days 0, 3, 7, 14, 28 in addition to baseline)

Exploratory objective:

- To assess the correlation between SARS-CoV-2 PCR positivity from nasal swab specimens, based on RT PCR, and detection of viable SARS-CoV-2 from nasal swab specimens based on viral culture assays

Serious adverse events, and grades  $\geq 3$  adverse events will be monitored during the study period.

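### The enhancement count and its interim comparison use only an indication for mechanical ventilation, so a death with no prior indication is a non-event there.

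*Combined protocol and SAP*

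**What the plan says.** Section 7.3 (Halting Criteria for the Study) adds a monitoring step aimed at antibody-mediated enhancement (ADE), on top of its six numbered halting criteria. It has three stages, all tied to one event.

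- **The count.** The protocol says "we will monitor the number of subjects in each trial arm that progresses to an indication for need of mechanical ventilation".
- **The formal question.** The timing is set as follows: "After at least 50% of trial participants have accumulated follow-up, the number of subjects that progress to this stage will be presented". The recipient is the DSMB, still masked, which must say whether it sees a difference that warrants unmasking and, if so, a formal interim analysis.
- **The interim analysis.** If one is requested, "we will examine the difference in treatment arms for need for mechanical ventilation". On covariates: "This interim analysis will adjust for factors related to need for mechanical ventilation including age and presence of cardiopulmonary comorbidities".

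Death is named at none of these stages, and no rule covers a participant who dies before reaching an indication.

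Death does appear in the halting criteria. Criterion 1 is "Unexpected death of a dosed subject in relation to infusion" and criterion 3 is "One subject with an unexpected SAE associated with study product". Under Assessment of Association in Section 6.7, an event can be rated not associated if "the event appears to be explained by another etiology".

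The severity scale in Section 3.1 keeps the two outcomes apart: category 6 is "Requiring mechanical ventilation and/or in ICU" and category 7 is death.

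**The concern.** Death is a competing event for ventilation. A participant who dies first leaves the pool that could still reach an indication, and under the Section 7.3 definition stays a non-event. In a harm comparison this omission works in the unsafe direction. If enhancement made some plasma recipients deteriorate and die quickly, or die at home, the monitored count in the plasma arm would not rise with those deaths.

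The event-by-event safeguards are weakest for this kind of harm. Enhanced COVID-19 looks like COVID-19, so an investigator can reasonably attribute such a death to the disease, and criteria 1, 3 and 4 then do not apply. What reveals the harm is a comparison between arms that needs no attribution. The ventilation count is the comparison the plan sets up for enhancement, and it omits the worst outcome.

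At stake is whether the DSMB's formal decision to unmask, and the interim analysis that may follow, rest on an event that can miss fatal enhancement.

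**Working it through.** **Step 1. Inputs**

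- Size and allocation (Section 3.1): 150 participants, up to 100 plasma and 50 control. Half follow-up is 75, or 50 plasma and 25 control if the 2:1 ratio holds at that point.
- Rates (Table 2), control and plasma. Scenario 1: ICU/ventilation 5% and 3%, death 5% and 2%. Scenario 2: ICU/ventilation 2% and 1%, death 2% and 1%.
- Share *f* of deaths with no prior ventilation indication: not in the documents. Assumed to be 10% to 50%, with the extremes shown in Step 5.

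**Step 2. The plan's own figure.** The plan states no figure for the ventilation monitoring. The Table 2 rates are those behind its stated power of 74% and 80%. Simulating the tie-corrected Mann-Whitney test (100 v 50, one-sided 0.15, 8,000 runs) gives 75.2% unstratified and 74.1% with two strata in Scenario 1, and 80.3% and 81.1% in Scenario 2. Whitehead's formula gives 73.8% and 79.4%. The table has therefore been read as intended.

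**Step 3. Expected deaths at half follow-up**

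- Scenario 1: 25 × 0.05 + 50 × 0.02 = 1.25 + 1.00 = 2.25
- Scenario 2: 25 × 0.02 + 50 × 0.01 = 0.50 + 0.50 = 1.0

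**Step 4. Expected category 6 or 7 outcomes**

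- Scenario 1: category 6 is 25 × 0.05 + 50 × 0.03 = 2.75; with deaths, 2.75 + 2.25 = 5.0
- Scenario 2: category 6 is 25 × 0.02 + 50 × 0.01 = 1.0; with deaths, 1.0 + 1.0 = 2.0

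**Step 5. What the present definition misses.** Missed events = *f* × deaths. Share missed = missed events ÷ category 6 or 7 outcomes.

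| *f* | Scenario 1 missed | Share | Scenario 2 missed | Share |
|---|---|---|---|---|
| 0 | 0 | 0% | 0 | 0% |
| 0.10 | 0.225 | 4.5% | 0.10 | 5% |
| 0.50 | 1.125 | 22.5% | 0.50 | 25% |
| 1 | 2.25 | 45% | 1.0 | 50% |

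**Step 6. Count before and after adding death.** People who reach an indication and then die are already counted. The present count is therefore about category 6 + (1 − *f*) × deaths.

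- Scenario 1: from 2.75 + 0.5 × 2.25 = 3.875 to 2.75 + 0.9 × 2.25 = 4.775, against 5.0 with death added
- Scenario 2: from 1.0 + 0.5 × 1.0 = 1.5 to 1.0 + 0.9 × 1.0 = 1.9, against 2.0

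**Step 7. Without an assumed benefit.** The plasma columns of Table 2 assume that plasma works, which is not the situation this monitoring is for. With both arms at the control rates:

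- Scenario 1: 75 × 0.05 = 3.75 deaths, of which 0.375 to 1.875 are missed out of 75 × 0.10 = 7.5 outcomes
- Scenario 2: 75 × 0.02 = 1.5 deaths, of which 0.15 to 0.75 are missed out of 75 × 0.04 = 3.0 outcomes

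The share is 5% to 25% in both.

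**Limits of the proxy.** Table 2 gives status on Day 28 or at the last rating, whereas the monitored event is ever reaching an indication. Category 6 includes ICU stay without ventilation, which Section 7.3 does not count, and leaves out people who were ventilated and had recovered by Day 28, whom it does count. The shares are approximate for that reason.

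**The case against.** The strongest case against is that the ventilation count is an extra layer and the DSMB is not blind to deaths. A death is an SAE (Section 6.7). Cumulative SAE incidence is a primary safety endpoint, and Section 3.2 compares SAEs between arms by Fisher's exact test. Death is the worst category of the primary scale, and time to death is a secondary outcome. Section 7.1 gives the DSMB a quarterly review of safety and efficacy. Halting criterion 5 lets it act on a pattern of events, and criterion 6 covers any other event that the responsible physician judges serious, with no requirement of association. A respiratory signal specific to enhancement is also a defensible choice.

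All of this stands, and it rules out several stronger readings that a reader might infer.

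- *Every death without ventilation goes uncounted.* The event is an indication for ventilation, not its use. Someone who meets the indication and dies unventilated is counted.
- *The trial treats these participants as unharmed.* That is true only of this count and its interim comparison.
- *Adding death would nearly double the count, from 2.75 to 5.0.* That takes final-status category 6 as the present count and ignores people who reached an indication before dying. Under the assumed range, Step 6 shows a gain of about 0.2 to 1.1 events in Scenario 1.
- *Leaving out ICU care without ventilation is a comparable fault.* It is not. Adding it is optional and does nothing for the competing-event problem.

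The objection does not reach the prespecified comparison itself. Criteria 5 and 6 rest on judgement. The quarterly review names no comparison of deaths by arm. The Fisher and Cox analyses in Section 3.2 have no stated role in the interim decision. The question that triggers unmasking, and the analysis that follows, remain tied to ventilation need.

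**Conclusion.** The point holds in this limited form: the Section 7.3 enhancement count, the formal DSMB question and the triggered interim analysis leave out death and do not say how a death before a ventilation indication is handled. Such a death cannot raise the count in either arm.

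In expected events the gap is small: about 0.2 to 1.1 at half follow-up in Scenario 1 and 0.1 to 0.5 in Scenario 2. As a share of the worst outcomes it is not negligible, roughly 4.5% to 25%, because Table 2 expects deaths about as often as ICU or ventilation. These figures rest on the assumed 10% to 50% of deaths with no prior indication, on Table 2 rates, on a 50 v 25 split at half follow-up, and on category 6 as an approximate stand-in for ventilation need. If every death were preceded by an indication, nothing would be missed.

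The documents do not support saying that fatal harm would go unseen in this trial. They support saying that the comparison designed to detect enhancement can miss its fatal form. That makes this an inexpensive improvement worth making, and it does not undermine the trial's overall safety oversight.

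**What to change.** In Section 7.3, define the monitored event as an indication for mechanical ventilation or death from any cause, whichever comes first. Use it for the masked DSMB display, the formal question at half follow-up and any interim analysis. Show the two components by arm beside the combined count, so that the DSMB can see whether a difference comes from ventilation or from death.

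The wording changes in three places (the count, the formal question and the interim comparison), and the covariate sentence should refer to factors related to the combined event. No new data are needed: the Schedule of Events already has disease severity assessed at follow-up visits through Day 60, and deaths are reported as SAEs.

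The cost is some noise, because deaths unrelated to enhancement will be included. Randomisation balances these between arms in expectation, and the component display keeps the respiratory signal visible.
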